## 7.5.3 **Day + 2 (Discharge and transition to outpatient treatment)**

- The assessments listed below are completed before discharge
- CTNI to conduct interviews for HAMD17
- Conduct interviews for CGI-I
- EPDS
- STAI6
- Collect AEs
- Collect ECG
- Collect VS (BP, pulse, respiratory rate, pulse oximetry, temperature)
- Collect SSS
- Collect a pharmacokinetic sample at 8 am (23h)
- Collect neurosteroid level
- Record concomitant medications
- Conduct CSSRS interview
- Perform physical examination
- Dispense medication bottle
- Provide the subject with dosing instructions and subject diary completion.
- Subject will take the IP (900 mg dose of ganaxolone, or matching placebo) at dinner time (four 225 mg capsules, or matching placebo capsules)

## 7.6 Outpatient treatment phase (Days + 3 – +29) - Cohort 6

## 7.6.1 Safety phone calls (Days +3, +5, +10 and +13)

• A safety phone call is made on days +3, +5, +10, and +13 by the PI (or the sub-I). The subject is asked about her general wellbeing. AEs are recorded.

### 7.6.2 **Visit 3 HAMD Call (Day +4 ±1 day)**

• CTNI to conduct HAMD17 interview

## 7.6.3 Visit 4 (Day +8)

- CTNI to conduct HAMD17 interview
- EPDS
- STAI6
- Assess CGI-I
- Review concomitant medications and therapies
- Collect vital signs (BP, pulse, temperature, pulse oximetry, respiratory rate),
- Collect ECG
- Collect urine sample for urinalysis, drug screen and urine pregnancy test
- Collect safety laboratory tests
- Collect neurosteroid level
- Collect a pharmacokinetic sample
- Stanford Sleepiness Scale (SSS)
- Conduct CSSRS interview
- Collect AEs
- Dispense study medication with a supply to last until the next visit (+ 3 days overage to cover for unexpected need to re-schedule a study visit or weekends). Provide the subject with dosing instructions. IP return and accountability.
- Subject will continue to take study drug (900 mg of ganaxolone, or matching placebo) at dinner time (unless the dose is lowered to 675 mg, or 450 mg, or matching placebo at dinner time as per instructions from the investigator)

### 7.6.4 Visit 5 HAMD Call (Day +11 ±1 day)

• CTNI to conduct HAMD17 interview

## 7.6.5 Visit 6 (Day +15 ±2 days)

- CTNI to conduct HAMD17 interview
- EPDS
- STAI6
- Assess CGI-I
- Review concomitant medications and therapies
- Collect vital signs (BP, pulse, temperature, pulse oximetry, respiratory rate),
- Collect ECG

- Collect urine sample for urinalysis, drug screen and urine pregnancy test
- Collect safety laboratory tests
- Collect neurosteroid level
- Collect a pharmacokinetic sample
- Measure weight
- Stanford Sleepiness Scale (SSS)
- Conduct CSSRS interview
- Collect AEs
- Dispense study medication with a supply to last until the next visit (+ 3 days overage to cover for unexpected need to re-schedule a study visit or weekends). Provide the subject with dosing instructions. IP return and accountability.
- Perform physical examination

### 7.6.6 Visit 7 (Day +22 ±3 days)

- CTNI to conduct HAMD17 interview
- EPDS
- STAI6
- Assess CGI-I
- Review concomitant medications and therapies
- Collect vital signs (BP, pulse, temperature, pulse oximetry, respiratory rate),
- Collect ECG
- Collect urine sample for urinalysis, drug screen and urine pregnancy test
- Collect neurosteroid level
- Collect a pharmacokinetic sample
- Stanford Sleepiness Scale (SSS)
- Conduct CSSRS interview
- Collect AEs
- Dispense study medication with a supply to last until the next visit (+ 3 days overage to cover for unexpected need to re-schedule a study visit or weekends). Provide the subject with dosing instructions. IP return and accountability.

## 7.6.7 Visit 8 (Day +29 ±3 days)

• CTNI to conduct HAMD17 interview

- EPDS
- STAI6
- Assess CGI-I
- Review concomitant medications and therapies
- Collect vital signs (BP, pulse, temperature, pulse oximetry, respiratory rate),
- Collect ECG
- Collect urine sample for urinalysis, drug screen and urine pregnancy test
- Collect safety laboratory tests
- Collect a pharmacokinetic sample
- Measure weight
- Stanford Sleepiness Scale (SSS)
- Conduct CSSRS interview
- Collect AEs
- Dispense study medication with a supply to last through the taper period. Provide the subject with dosing instructions. IP return and accountability.
- Begin 3-day taper (3 capsules on Day 29, 2 capsules on Day30, 1 capsule on Day31, or, if Day 28 dose is other than ganaxolone 900 mg or placebo, follow instructions in section 3.4.6)
- Perform physical examination

# 7.7 Post-treatment Follow-up Period (Days +29 to +71) – Cohort 6

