#### 3.4.5 **Cohort 6**

For Cohort 6, the goal of initiation of treatment with IV infusion followed by oral capsules is to maximize the speed of onset of antidepressant activity while providing the convenience of oral dosing for the remainder of the treatment period. Under this IV-oral dosing schedule there may not be a need for a prolonged inpatient observation.

This initial infusion is targeted to provide a fast onset of antidepressant activity by delivery of rapid plasma exposures to ganaxolone. At dinner time of Day 1 the subjects will take their first oral dose of ganaxolone 900 mg or matching placebo (4 capsules). This dose is expected to provide mean  $C_{max}$  plasma concentrations of approximately 250-300 ng/mL and mean steady-state levels between 90 and 150 ng/mL, which may be mildly sedating. In previous studies ganaxolone has been given up to a daily dose of 2000 mg, and at single doses of 1000 mg. Based on the previous experience this dose is expected to be safe.

At subsequent nights (Days 2-28), the target dose is ganaxolone 900 mg or matching placebo (4 capsules) at dinner time followed by a 3-day taper (3, 2, and 1 capsule/s per day, respectively). However, based on the assessment of the investigator the dose may be maintained at 675 mg or 450 mg (or matching placebo) in case of adverse events, such as grogginess in the morning. In the case of 3 capsules per day on day 28 the taper will consist of 2, 2, and 1 capsule/s on days 29, 30, and 31, respectively. In the case of 2 capsules per day on day 28 the taper will consist of 1 capsule on days 29, 30, and 31. If the subject cannot tolerate 450 mg (or matching placebo) per dose the investigator will contact the Medical Monitor to discuss dosing options.

Subjects will be provided with a diary to capture the details of dose administration and associated food intake throughout the treatment period. Subjects will document the number of capsules taken and whether a fatty meal/snack (e.g., fatty yogurt, nuts, avocado) was consumed  $\pm 15$  minutes of taking the capsules.

The mechanism by which ganaxolone is postulated to be efficacious under this dosing regimen is restructuring of sleep architecture. Preclinical studies have shown that allopregnanolone has the capacity to modulate sleep, and disturbed sleep architecture is one of the hallmarks of depression.

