taper (3, 2, and 1 capsule/s per day, respectively (unless the dose is adjusted as per the instructions from the investigator in which case the taper follows instructions in section 3.4.6).

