## 6.2.4 **Dose Adjustments**

Sedation and dizziness are known effects of ganaxolone at higher doses. If a subject experiences excessive sedation or dizziness the investigator may adjust the dosing by stopping the infusion for a minimum of 1 hour or until the effects resolve and then restarting the dosing at half the rate prescribed for the cohort (for Cohorts 1-5). For example, if the rate prescribed for the cohort is 4 mg/h (16 ml/h), the investigator may stop the infusion for 1 hour and then restart the infusion at 2 mg/h (8 ml/h). If the dose is adjusted, this must be recorded in the source documentation and eCRF. Under these circumstances the subject must be monitored closely for recurrence of sedation.

If the subject experiences excessive sedation or dizziness during the administration of the bolus dose, the dosing should be stopped immediately. The investigator should wait for a minimum of 1 hour or until the effects resolve and then starting the infusion at the rate prescribed for the cohort. Under these circumstances the subject must be monitored closely for recurrence of sedation. The dose of the oral medication in Cohort 6 may be adjusted by lowering the dose from 900 mg to 675 mg or 450 mg, or matching placebo at dinner time if the subject experiences adverse effects, such as sedation in the morning. If the dose is adjusted, this must be recorded in the eCRF. Other dosing adjustments may be possible, but they should be discussed with the medical monitor.

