# 7.0 STUDY PROCEDURES

This is a Phase 2A, double-blind, placebo-controlled, multiple-dose escalation study consisting of up to 6 cohorts. In Cohorts 1-5 the IV formulation of ganaxolone will be used while in Cohort 6 both IV and oral formulations will be used. Approximately 200 women with PPD 18 to 45 years of age will be screened to randomize approximately 100 subjects across the up to 6 cohorts. Approximately 10-30 subjects will be randomized into each cohort. Randomized subjects will receive ganaxolone or placebo in a 1:1 ratio. In Cohorts 1-5 the treatment is administered intravenously (with or without an initial bolus) over 60 hours. In Cohort 6 the treatment is initiated with a 6-hour intravenous (IV) infusion followed by oral ganaxolone or matching placebo. Additional subjects may be included into these cohorts or additional cohorts may be added, but will not exceed 100 randomized subjects for the study.

The screening period for each cohort will be up to 2 weeks. Following the screening period, there will be a 4-day inpatient treatment phase at a hospital or clinical pharmacology unit for Cohorts 1-5 during which a 60-hour infusion of ganaxolone or placebo will be administered (with or without bolus dosing). The subjects will be discharged from the unit on the morning of Day 4. There will be 2 safety follow-up visits after inpatient discharge on post-treatment Weeks 1 and 4.

[figure not shown]
In Cohort 6, following the screening period, there will be a 1-day inpatient treatment phase at a hospital or clinical pharmacology unit during which a 6-hour infusion of ganaxolone or matching placebo will be administered initially from 9 am to 3 pm ( $\pm$ 1 hour) before oral dosing is started at 7 pm ( $\pm$ 1 hour). The subjects will be admitted on Day 0 and discharged from the unit in the morning of Day 2. The first dose of oral ganaxolone (4 capsules; 900 mg) or matching placebo will be administered at dinner time (around 7 pm) of Day 1, 4 hours after the end of infusion on Day 1. Oral dosing is continued as outpatient on Days 2-28. The dosing regimen during the outpatient phase of Cohort 6 is 900 mg or placebo (4 capsules) at dinner time daily. A 3-day taper will follow at days 29, 30, and 31, as described in Section 3.4.6. There will be 3 safety follow-up visits after the last dose on post-treatment Weeks 1,4, and 6.

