On Day 1 subjects will have 6 PK samplings: at 1 hour after the end of the 6-hour infusion (i.e., at 4 pm), at 7 pm (just prior to the oral dosing), and at 1, 2, 3, and 4 hours post oral dosing (at 8, 9, 10, and 11 pm) as well at 8 am the following morning (on Day 2) prior to discharge.

The subjects will take a 900 mg dose or placebo (4 caps) on the evening of Day 1 at dinner time and continue with the 900 mg dose or matching placebo at dinner time on Days 2-28. A 3-day taper will follow as described in Section 3.4.6.

A schematic of the study design if provided in Figure 1.

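### The Cohort 6 taper instructions for dose-reduced women point to Protocol Section 3.4.6, which contains no taper; the rule is in Section 3.4.5

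*Protocol*

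**What the plan says.** The standard Cohort 6 regimen is 4 capsules (900 mg ganaxolone, or placebo) daily to Day 28, then 3, 2 and 1 capsules on Days 29, 30 and 31. The investigator may lower the dose to 3 capsules (675 mg) or 2 capsules (450 mg) for adverse effects.

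Two instructions govern the taper for women on a lowered dose:

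- Protocol 6.2.3 (Dosing, Cohort 6) gives the 3-2-1 taper "unless the dose is adjusted as per the instructions from the investigator in which case the taper follows instructions in section 3.4.6".
- Protocol 7.6.7 (Visit 8) prints 3-2-1 and adds "if Day 28 dose is other than ganaxolone 900 mg or placebo, follow instructions in section 3.4.6".

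Two general statements in Protocol 7.0 use the same section number: "A 3-day taper will follow at days 29, 30, and 31, as described in Section 3.4.6" and "A 3-day taper will follow as described in Section 3.4.6".

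The rule itself is in Protocol 3.4.5 (Cohort 6): "In the case of 3 capsules per day on day 28 the taper will consist of 2, 2, and 1 capsule/s" on Days 29 to 31, and "In the case of 2 capsules per day on day 28 the taper will consist of 1 capsule on days 29, 30, and 31". For women below that level the section gives no taper: "If the subject cannot tolerate 450 mg (or matching placebo) per dose the investigator will contact the Medical Monitor to discuss dosing options".

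**The concern.** Section 3.4.6 reports peak concentrations, sedation scores and adverse events from a Phase 1 study of IV ganaxolone in healthy volunteers. It contains no taper, no capsule count and no rule for reducing the oral dose. A site that follows either instruction for a dose-reduced woman therefore finds nothing there.

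Visit 8 is where this matters. Staff dispense the taper supply and give the dosing instructions at that visit, and the woman then tapers at home. The safety calls are on Days 3, 5, 10 and 13, and the next scheduled visit is Day 36, so no planned contact after Visit 8 would catch a wrong instruction during the taper. The women affected are those whose dose was lowered for effects such as morning sedation. The only taper printed in full at Visit 8 is 3-2-1, which is the wrong one for them.

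**Working it through.** **Cross-reference check.** Each place in the current protocol body that cites Section 3.4.6 for the taper, set against what that section holds:

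| Place | Purpose | Section cited | Taper found there? |
|---|---|---|---|
| 6.2.3 | adjusted dose | 3.4.6 | no |
| 7.6.7, Visit 8 | Day 28 dose not the standard one | 3.4.6 | no |
| 7.0, first | taper in general | 3.4.6 | no |
| 7.0, second | taper in general | 3.4.6 | no |

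None of the four reaches a taper. The table of contents numbers 3.4.5 and 3.4.6 as the body does, so the mismatch lies in the protocol and not in the text extraction. The two pointers in 7.0 follow the standard 900 mg regimen, whose 3-2-1 taper is printed elsewhere (3.1, 3.3, 6.2.3, 7.6.7), so nothing is lost there. Section 6.2.4 allows the lower doses but gives no taper for them, and the SAP (6.1 and 8.1) prints only 3-2-1.

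**Size if a site fell back on 3-2-1.** The protocol gives no figure to reproduce. The inputs are 225 mg per capsule (Protocol 6.1.3), the printed 3-2-1 taper (7.6.7) and the reduced-dose tapers (3.4.5). Dose = capsules × 225 mg.

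| Taper | Day 29 | Day 30 | Day 31 | Total |
|---|---|---|---|---|
| 3-2-1 | 675 | 450 | 225 | 1350 mg |
| 3.4.5, from 3 capsules (675 mg) | 450 | 450 | 225 | 1125 mg |
| 3.4.5, from 2 capsules (450 mg) | 225 | 225 | 225 | 675 mg |

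From 2 capsules:

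- Excess by day: 675 − 225 = 450, 450 − 225 = 225, 225 − 225 = 0; in all 675 mg.
- Ratio of totals: 1350 / 675 = 2.0.
- Day 29 step under the rule: 225 − 450 = −225 mg. Under the fallback: 675 − 450 = +225 mg.

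From 3 capsules:

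- Excess by day: 675 − 450 = 225, 450 − 450 = 0, 225 − 225 = 0; in all 225 mg.
- Ratio of totals: 1350 / 1125 = 1.2.
- Day 29 step under the rule: 450 − 675 = −225 mg. Under the fallback: 675 − 675 = 0.

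The highest dose on any day is 675 mg. Women on placebo receive no drug under either taper.

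**The case against.** The strongest reply is that this is a one-digit pointer error with a complete rule close by. Section 3.4.5 states a single reduced-dose taper, nothing in the protocol contradicts it, and it comes immediately before the section cited. The change log in Appendix 3 also reprints the rule under its correct number. Both 6.2.3 and 7.6.7 already say that an adjusted dose does not follow 3-2-1, so a site that found nothing in 3.4.6 should look nearby or telephone; 6.2.4 offers that route: "Other dosing adjustments may be possible, but they should be discussed with the medical monitor". The excess doses calculated above arise only if a site acts against the text.

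Most of this stands and limits the size of the point. The dose figures are a conditional worst case, not a forecast. The two pointers in 7.0 belong on the correction list but add no weight. The capsule-count wording below is an improvement in clarity; *ganaxolone 900 mg or placebo* at Visit 8 is most likely shorthand for 4 capsules in either arm and is not a separate defect.

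It does not remove the point. A change log is not operating text, and an instruction at the visit where the taper is dispensed should lead to the rule it invokes.

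**Conclusion.** The concern holds. Both instructions for women on a reduced dose cite a section with no taper, and so do the two general pointers. The protocol body states the reduced-dose rule only in Section 3.4.5. It should be corrected because it is a dosing instruction that does not work as written, for women who had adverse effects and who taper at home.

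The risk is small and depends on a site using 3-2-1 despite the wording. In that case the excess is 675 mg over two evenings from a 450 mg dose, or 225 mg on one evening from a 675 mg dose, always within a permitted daily dose. The documents do not say how many women are on a reduced dose at Day 28, so no expected number affected can be given. No analysis, power or error rate is affected.

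**What to change.** Change 3.4.6 to 3.4.5 in Protocol 6.2.3, in both places in 7.0, and in 7.6.7.

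Word the Visit 8 condition by capsule count, which blinded staff can apply without knowing the arm. For example: *if the Day 28 dose is 3 or 2 capsules (either arm), follow the taper in Section 3.4.5; if fewer than 2 capsules, contact the Medical Monitor.* The last clause follows what 3.4.5 already says about women who cannot tolerate 450 mg. No new taper has to be chosen.

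The cost is four section numbers and one clause, by amendment or a clarification letter to sites, before Cohort 6 women reach Day 28. It needs no extra visits or supplies and no change to the SAP.

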## 7.7.1 First Post-treatment Follow-up Visit - 7 days After the Last On-treatment Visit (Day +36)

- The Follow-up Visit 1 should occur about 1 week after the Day 29 visit.
- CTNI to conduct interviews for HAMD17
- Perform EPDS
- Perform STAI6
- Assess CGI-I
- Review concomitant medications and therapies
- Collect vital signs (BP, pulse, temperature, RR)
- Collect ECG Collect neurosteroid level
- Collect a pharmacokinetic sample
- Collect urine sample for urinalysis, drug screen and urine pregnancy test
- Measure weight

- Conduct CSSRS interview
- Collect SSS
- Collect AEs
- IP return and accountability

# 7.7.2 Second Post-treatment Follow-up Visit - 28 days After the Last Ontreatment Visit (Day +57)

- The Follow-up Visit 2 should occur about 28 days after the Day 29 visit.
- CTNI to conduct interviews for HAMD17
- Perform EPDS
- Perform STAI6
- Assess CGI-I
- Review concomitant medications and therapies
- Collect vital signs (BP, pulse, temperature, RR)
- Collect safety laboratory tests
- Collect urine sample for urinalysis, drug screen and urine pregnancy test
- Measure weight
- Conduct CSSRS interview
- Collect SSS
- Collect AEs

# 7.7.3 Third Post-treatment Follow-up Visit - 42 days After the Last On-treatment Visit (Day +71)

- The Follow-up Visit 3 should occur about 42 days after the Day 29 visit.
- CTNI to conduct interviews for HAMD17
- Perform EPDS
- Perform STAI6
- Assess CGI-I
- Review concomitant medications and therapies
- Collect vital signs (BP, pulse, temperature, RR)
- Collect urine sample for urinalysis, drug screen and urine pregnancy test
- Measure weight
- Conduct CSSRS interview
- Collect SSS
- Collect AEs

# Table 2. Schedule of Assessments - Cohort 6

Day	Day -14 to -1	Day 0 Admission	Day 1	Day 1 e	Day 2 f	Days 3 & 5	Day 4	Day 8	Days 10 & 13	Day 11	Day 15	Day 22	Day 29	Contraction (Section	17	100 BEA
VISIT	Screenin g		Baseline	Post-BL	Discharge & Outpatient	Safety call	V3 HAMD Call	V4 outpt	0-6-4-	V5 HAMD Call	V6 outpt	V7 outpt	V8 outpt	l st Follow- up	2 nd Follow- up	3 rd Follow- up
Informed consent	X															
Demographics, Medical History	X								10 10							-0
MINI neuropsychiatric interview	X											o				
Inclusion/Exclusion criteria	X	X														
Concomitant Meds and Therapy Review	X	X	X	X	X			X			Х	X	X	X	X	X
Admission to the unit		X														
Discharge from the unit					X			0			2	2 				N
Physical examination	X				X						X		X			
SAFER Interview (during screening)	X															
Vital signs (BP, Pulse, pO2, RR, temp)	X	X	X	X	X			X			Х	Х	X	X	X	X
Height (screening only) and weight	X	X		0.				0	2		X	5	Х	X	Х	X
ECGs	X	X		X	X			x			X	X	x	x		
Safety Laboratory Tests	X	X						x			X		X		X	
Neurosteroid level		X		X	X			X			X	X		X		
Urinalysis, Drug Screen and Pregnancy Tests	X	X		· .				X	2		Х	X	X	X	X	X
CSSRS	X	X	X	X	X			x	· · · ·		X	X	X	X	X	X
Record AEs		X	X	X	X	X		x	X		X	X	X	X	X	x
Randomization			X													
Start infusion (0h; 9 am $\pm$ 1h) a	-	)		X				0	3							0
End infusion (6h)	.a .c.	22		X							0 X0	07.			2	
PK sample collection b				X	X			X			X	X	X	X	1	Ť
HAMD17 c	X	X	X	x	X		x	X		X	X	X	X	X	X	X
CGI-I		)		X	X			X	1997 1997		X	X	X	X	X	X
CGI-S	X	27.	X								0 X0	02				-
EPDS	X		x	X	X			x			x	X	X	X	X	x
SSS			x	X	X			x			X	X	X	X	X	x
STAI6	X	54. 	X	X	X			x	a		x	X	x	X	X	x
Dispense medication/return accountability	a 75	C.Y			X			x	9		x	X	X			
Oral dosing (at dinner time)				X			ť	hroughout	the outpa	tient perio	d	11 75878 G	0.870			
Q15 min health checks & pulse ox d		X	through	out the inpa	tient period			[	•				1			
Start 3-day taper		i la contra c										64	x			.

a Infusion starts at 9 am and ends 6 hours later at 3 pm and is administered at a constant rate of 40 mL/hr.

b Twelve pharmacokinetic samples are collected in Cohort 6:

On Day 1 subjects will have 6 PK samplings: at 1 hour after the end of the 6-hour infusion (i.e., at 4 pm), at 7 pm (just prior to the oral dosing), and at 1, 2, 3, and 4 hours post oral dosing (at 8, 9, 10, and 11 pm) as well at 8 am the following morning (on Day 2) prior to discharge.

A pharmacokinetic sample is also collected on Days 8, 15, 22, 29, and 36 during the study visit.

c All HAMD17 ratings, except the one done at screening, will be conducted by CTNI raters.

 $^{d}$ Q15min health checks are done from the time of start of the infusion to the time of discharge. Pulse oximetry (pO2) must be monitored from the start of the infusion throughout the inpatient period, including during the night when the subject is sleeping. The subject should be awakened if pulse oximetry falls < 91%.

e On Day +1 all efficacy assessments should be conducted first before lab draws, if possible.

f All Day +2 assessments, including PK and neurosteroid levels, are to be done before the subject is discharged from the unit.

The following priority order will be in effect when more than 1 assessment is required at a particular time point: 1) HAMD17 2) CGI-I/CGI-S 3) EPDS 4) STAI6 5) SSS 6) CSSRS 7) vital signs 8) ECG 9) safety labs and neurosteroid level 10) PK sample 11) neurosteroid level 12) urinalysis drug screen and pregnancy test 13) physical examination

All outpatient visits have  $a \pm 3$ -day visit window, except Visits 3 and 5 which have just  $a \pm 1$ -day visit window and Visits 4 and 6 which have  $a \pm 2$ -day visit window.

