#### 6.2 Administration of Investigational Product(s)

For administration of the IV investigational product (IP; ganaxolone or matching placebo [0.9% saline solution]) the investigator needs to use the Sponsor-approved Captisol®-compatible

intravenous infusion bags and infusion sets which are prepared according to the Pharmacy manual. Any substitutions and deviations from the Pharmacy manual need to be approved by the sponsor.

Ganaxolone or matching placebo capsules (Cohort 6 only) will be administered orally with food. Ganaxolone or matching placebo capsules should be taken  $\pm 15$  minutes of a fatty meal or snack (e.g., fatty yogurt, nuts, avocado) and with 240 mL (8 oz) of water at dinner time.

Subjects will be provided with a diary to capture the details of dose administration and associated food intake throughout the treatment period. Subjects will document the number of capsules taken and whether a fatty meal/snack (e.g., fatty yogurt, nuts, avocado) was consumed  $\pm 15$  minutes of taking the capsules.

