# 9.5.10 Pharmacokinetic Analyses

The following pharmacokinetics parameters will be estimated for each subject receiving ganaxolone, if sufficient data are available: Maximal plasma concentration ( $C_{max}$ ), concentration at steady-state ( $C_{ss}$ , determined by the mean concentrations once steady-state is achieved by visual inspection), AUC0-24 (calculated as  $C_{ss}$  multiplied by 24 hours). PK samples will be collected from subjects participating in Cohort 6 after the IV infusion, before and during the oral dosing portion of the study.

CONFIDENTIAL

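### Cohort 6 outpatient PK samples on Days 8, 15, 22 and 29 have no specified or required-to-be-recorded time since dose, yet Css and AUC0-24 have no separate rule for the oral phase

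*Protocol*

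**What the plan says.** **Outpatient draws.** Protocol 7.8.8 refers to Tables 1 and 2 for PK sampling times. For the Cohort 6 outpatient phase, Table 2 footnote b gives: "A pharmacokinetic sample is also collected on Days 8, 15, 22, 29, and 36 during the study visit". The visit lists in 7.6.3 and 7.6.5 to 7.7.1 call for one PK sample and give no hour.

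**Outpatient doses.** Section 6.5.2 has the capsules taken at home at dinner time, with no clock time. Section 6.2 provides a diary for the details of dose administration and food intake, then names the items: "Subjects will document the number of capsules taken and whether a fatty meal/snack" was eaten within 15 minutes either way. Section 6.3.2.2 describes the diary as documenting intake of the product and the fatty food. The clock time of the dose is not named anywhere.

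**Derived exposure.** Section 9.5.10 has Css "determined by the mean concentrations once steady-state is achieved by visual inspection", and AUC0-24 as Css multiplied by 24 hours. It gives no separate rule for the oral phase. The SAP (4.0, 5.0) leaves PK analysis out of scope.

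**Day 1 draws.** Footnote b words these by event and attaches clock times: "at 1 hour after the end of the 6-hour infusion (i.e., at 4 pm), at 7 pm (just prior to the oral dosing"), then 1, 2, 3 and 4 hours after the oral dose with 8, 9, 10 and 11 pm in brackets. Section 7.5.2 uses the same events but labels the first two draws +7h and +10h. Section 7.0 allows 1 hour either way on both the infusion and the oral dose, and also places the oral dose "4 hours after the end of infusion on Day 1".

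**The concern.** The Day 1 and Day 2 draws cover only the first oral dose. All information on repeated oral dosing therefore comes from the four on-treatment outpatient draws. If their time since dose is not recorded, a difference between visits or between women may reflect only the hour of the appointment. It could be read as accumulation, missed capsules or a food effect.

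The Css rule makes this worse. Averaging concentrations over a plateau is sound for a 60-hour infusion, where the level is roughly constant. Between once-daily oral doses there is a peak and a decline, so the mean of a few draws taken 12 to 23 hours after dinner is not the 24-hour average, and multiplying it by 24 does not give AUC0-24.

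PK matters here. The study is meant to assess plasma exposure after IV and oral dosing (Protocol 2.2.3), to identify a safe and tolerated dose and exposure level (9.5), and to inform the regimen for further development (2.1). A dose time that was never written down cannot be restored at analysis.

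**Working it through.** **1. The plan's own counts and labels.** Day 1 has 1 post-infusion, 1 pre-dose and 4 post-dose draws, making 6. Day 2 adds 1 and the outpatient visits add 5: 6 + 1 + 5 = 12, as stated. At 6 mL each this is 72 mL, matching Table 4. From a 9 am start, the infusion ends at 3 pm, +7h is 4 pm, +10h is 7 pm and +23h is 8 am. All labels are right for a 9 am start and a 7 pm dose.

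**2. Which outpatient draws are on drug.** The last taper capsule is on Day 31 (7.0). Day 36 is 36 − 31 = 5 days later, or 2 to 8 days with the 3-day visit window. At most 4 of the 5 outpatient samples can be steady-state samples.

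**3. Is the oral profile flat?** Section 3.4.5 expects mean Cmax of 250–300 ng/mL and mean steady-state levels of 90–150 ng/mL. The ratio runs from 250/150 = 1.7 to 300/90 = 3.3. No half-life assumption is needed to see that it is not flat.

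**4. Effect of visit hour.** The documents give no oral half-life or clinic hours, so the following are assumptions: a 7 pm dose and visits from 9 am to 5 pm (14 to 22 h after dosing, an 8 h spread) with log-linear decline. The fold-difference is 2^(8/t½). Section 3.4.1 expects infusion steady state within 24 h; reading that as 4 to 5 half-lives gives 24/5 = 4.8 h to 24/4 = 6 h. Longer values are added to show the range.

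| Assumed half-life (h) | Fold-difference over 8 h |
|---|---|
| 4.8 | 3.17 |
| 6 | 2.52 |
| 12 | 1.59 |
| 20 | 1.32 |

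**5. Effect on Css × 24.** This uses a one-compartment model at oral steady state, with assumed absorption rate ka = 1/h, interval τ = 24 h, k = ln 2/t½ and dose/volume set to 1:

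C(t) = ka/(ka − k) × [e^(−kt)/(1 − e^(−kτ)) − e^(−ka·t)/(1 − e^(−ka·τ))], with 24-h average 1/(kτ).

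With dinners from 6 to 8 pm and visits from 8 am to 5 pm (again assumed), draws fall 12 to 23 h after the dose.

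| Assumed half-life (h) | C(12 h)/average | C(23 h)/average | C(12 h)/C(23 h) |
|---|---|---|---|
| 4.8 | 0.74 | 0.15 | 4.9 |
| 12 | 0.98 | 0.52 | 1.9 |
| 36 | 1.01 | 0.82 | 1.2 |

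If one such draw stood in for Css, Css × 24 would be 15–74% of the true AUC0-24 at 4.8 h, 52–98% at 12 h and 82–101% at 36 h. The error is mainly understatement and fades as the half-life lengthens.

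**6. Day 1 and 2 labels against the windows.** The infusion may start from 8 to 10 am and the oral dose may be given from 6 to 8 pm. A site following the label and not the event would draw:

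- the 7 pm pre-dose sample between 1 h before and 1 h after the dose;
- the 8 pm sample 0 to 2 h after the dose;
- the 4 pm sample 0 to 2 h after the end of infusion;
- the +10h sample up to 2 h either side of the dose if the two windows move independently, but exactly at the dose if the 4-hour gap in 7.0 is kept (6 + 4 = 10).

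The Day 2 draw at 8 am (23h) has no oral-dose anchor and falls 12 to 14 h after the dose.

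**The case against.** A reader might infer that Cohort 6 PK sampling in general is not tied to the dose, and that the pre-dose sample will often be post-dose. The documents do not support that. All six Day 1 draws are defined by the end of infusion or the oral dose, in Table 2 and in 7.5.2 alike, and the clock times are nominal equivalents. The dose is given on the unit, so a post-dose draw would mean ignoring the event wording in the same sentence. What remains is a minor ambiguity about which anchor governs.

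A reader might also infer that time since dose on Days 8 to 29 will be unknown. That too is more than the text shows. The diary is for details of dose administration, and the named items are not said to be exhaustive. The diary form and the PK eCRF page are not among the documents. PK analysis is assigned to other vendors (SAP 7.2.2), who may use actual times. Evening dosing with clinic visits also limits the draw to roughly half a day to a day after the dose. The supportable statement is that the time is neither specified nor required to be recorded.

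The fold-differences are illustrations. They carry a half-life inferred from an infusion over to an oral dose with food, and they need the same woman seen early at one visit and late at another.

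Finally, PK is descriptive. Parameters are estimated only if data suffice, and no test or sample size depends on them. That limits the consequence but does not remove it, because a concentration without its time since dose is hard to interpret even descriptively.

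**Conclusion.** The concern holds for the four on-treatment outpatient samples. Neither document fixes their time since dose or requires the two clock times needed to reconstruct it, and the Css and Css × 24 rule is not adapted to once-daily oral dosing. The protocol's own expected peak, 1.7 to 3.3 times its steady-state level, is enough to show that the rule can misstate oral exposure.

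How far depends on assumptions. For an 8 h spread in visit time it is about 2.5- to 3.2-fold at a half-life of 4.8–6 h and 1.3- to 1.6-fold at 12–20 h. If the half-life is long, or visits happen to fall at similar hours, the effect is small.

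The Day 36 sample is outside this point. The Day 1 label conflict is separate and minor. No efficacy or safety conclusion rests on either matter; what is at risk is the oral exposure description that is meant to inform the choice of regimen.

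**What to change.** 1. Add the clock time of each evening's capsules to the diary. On the PK eCRF page for Days 8, 15, 22 and 29, record the time of the last dose and the actual draw time. Record actual times for the Day 1 and Day 2 draws as well. If existing forms already capture these, say so in the protocol.
2. In Protocol 9.5.10, state that oral-phase concentrations are analysed by actual time since dose, and that the plateau Css and Css × 24 rule is not applied to untimed outpatient samples.
3. In Table 2 footnote b and Sections 7.0 and 7.5.2, state that event-relative times govern and that the clock and +10h times are nominal.

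Booking the PK visits at a consistent time of day would help but is optional. The cost is one diary field, one eCRF entry and a few lines of wording, with no extra samples. The diary field has to be in place before the outpatient doses it is meant to time.
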